7.6.3. Analysis of Time-to-Event Endpoints

Time-to-event analyses, such as time-to-first SLE flare and time-to-first BICLA response, will be analyzed using a Cox proportional hazards models adjusted for stratification factors (concomitant oral immunosuppressive therapy use at enrollment and geographic region). Subjects who do not experience the specified event will be censored on the date at which the last non-missing response data were collected. For example, in the time-to-first SLE flare, subjects who do not experience flares will be censored on the date of the last available BILAG value. In the analysis of time to first BICLA response, subjects who do not achieve a positive BICLA response will be censored on the date of their last non-missing BICLA response value. Estimated hazard ratios and corresponding 95% CI will be reported. If estimable, median, 25th and 75th percentiles of the time to specified event and corresponding 95% CI will be reported. Time to event secondary efficacy endpoints will be displayed in Kaplan-Meier curves.

7.7. Estimands for the Primary and Secondary Endpoints

Estimand definitions for the primary and secondary efficacy endpoints are provided below:

Table 2: Estimand Attributes Corresponding to the Primary and Secondary Efficacy Endpoints

	Attributes of the Estimand						
Estimand	Treatment	Endpoint	Population	Handling of Intercurrent Events	Statistical Summary		
Primary	ALPN-101 vs. Placebo	Achievement of SRI-4 response at Day 169	Subjects with moderate to severe SLE	IE1 and IE2: subject is considered a non-responder (composite strategy) Missing data: subject is considered a non-responder	Difference in the proportion of subjects achieving SRI- 4 response		
Primary	ALPN-101 vs. Placebo	Achievement of BICLA response at Day 169	Subjects with moderate to severe SLE	IE1 and IE2: subject is considered a non-responder (composite strategy) Missing data: subject is considered a non-responder	Difference in the proportion of subjects achieving BICLA response		
Secondary	ALPN-101 vs. Placebo	Annualized flare rate by BILAG- 2004 flare index through Day 169 for all flares	Subjects with moderate to severe SLE	All observed data used (treatment policy strategy)	Difference in the LS means for annualized flare rate by BILAG-2004 flare index for all flares		
Secondary	ALPN-101 vs. Placebo	Time-to-first flare by BILAG- 2004 flare index	Subjects with moderate to severe SLE	All observed data used (treatment policy strategy)	Hazard ratio for time-to- first flare by BILAG-2004 flare index		
Secondary	ALPN-101 vs. Placebo	Achievement of LLDAS response at Day 169	Subjects with moderate to severe SLE	IE1 and IE2: subject is considered a non-responder (composite strategy) Missing data: subject is considered a non-responder	Difference in the proportion of subjects achieving LLDAS response		

	Attributes of the Estimand						
Estimand	Treatment	Endpoint	Population	Handling of Intercurrent Events	Statistical Summary		
Secondary	ALPN-101 vs. Placebo	Change from baseline in SLEDAI-2K total score at Day 169	Subjects with moderate to severe SLE	All observed data used (hypothetical strategy)	Difference in the LS means for change from baseline in SLEDAI- 2K total score		
Secondary	ALPN-101 vs. Placebo	Cumulative prednisone- equivalent dose use through Day 169	Subjects with moderate to severe SLE	All observed data used (treatment policy strategy)	Difference in the LS means for cumulative prednisone- equivalent dose use		
Secondary	ALPN-101 vs. Placebo	Achievement of ≥50% reduction in CLASI activity score at Day 169 in the subgroup of subjects with baseline CLASI activity score ≥8	Subjects with moderate to severe SLE	IE1 and IE2: subject is considered a non-responder (composite strategy) Missing data: subject is considered a non-responder	Difference in the proportion of subjects achieving ≥50% reduction in CLASI activity score		

7.8. Analysis of Safety Endpoints

The primary study objective of assessing safety and tolerability of ALPN-101 in subjects with active SLE will be assessed using TEAEs, AEIs, SAEs, physical exam findings, vital signs, ECG measurements, and laboratory tests. All safety data will be descriptively summarized by treatment group. No formal inference is planned. Analyses will be based on subjects in the safety population. Individual subjects will only be counted once when calculating the incidence of AEs.

7.8.1. Treatment-Emergent Adverse Events

AEs will be recorded at all scheduled and unscheduled visits during the study. Summaries will be presented for TEAEs. In this study, signs and symptoms of SLE activity are captured in the disease activity assessments and will not be reported as AEs. Clinically significant changes in physical exam findings, laboratory test results, and ECG results will be recorded and analyzed as AEs. The incidence, seriousness, and severity of TEAEs and the relationship of the events to study drug will be used to assess safety.

All AEs terms will be classified using MedDRA and reported based on system organ classes and preferred terms. Adverse event severity will be graded using Common Terminology Criteria for Adverse Events (CTCAE), version 5.0. AEIs will be reviewed by the medical monitor lead.

In general, the incidence of AEs will be summarized by the number and the percentage of unique subjects in the safety population who experiencing an event. As such, subjects who report the

same event on multiple occasions will only be counted once. A by-subject listing of all AEs reported will be provided. Rules for the imputation of missing and partial AE dates and missing designations of AE severity, relatedness and seriousness are defined in Section 13.

7.8.2. Laboratory Tests

Safety laboratory tests collected in this study include hematology, serum chemistry, coagulation and urinalysis as specified Appendix 15.5. Numeric laboratory results that are reported using non-numeric qualifiers, such as less than (<) a certain value or greater than (>) a certain value, will be analyzed using the numeric portion of laboratory values minus one or plus one, respectively.

Descriptive summaries of continuous laboratory values and changes in these values from baseline will include the number of non-missing observations, mean, SD, median, min and max value at each scheduled visit, at the last on-treatment visit and at the end of study visit. Data will be summarized in standardized units.

The severity of laboratory result abnormalities will be graded using the CTCAE grading scale. Laboratory values that are within the limits of normal and are not graded as 1-4 will be summarized as a normal result with grade equal to 0. Treatment-emergent abnormal laboratory values are defined as those reported normal (i.e., grade=0) at baseline and abnormal (grade 1-4) after starting study medication. The numbers and percentages of subjects reporting a max (worst) treatment-emergent post-baseline grade observed through the end of the study will be summarized for each laboratory parameter. Percentages will be based on the number of subjects in the safety population with at least one post-baseline value of the respective laboratory parameter.

To examine hepatic laboratory parameters, additional summaries of alanine aminotransferase (ALT), aspartate aminotransferase (AST), total bilirubin and alkaline phosphatase (ALP) will be presented. The number and percentage of subjects in the safety population who meet the following criteria at any time during treatment or follow-up will be summarized:

- Peak ALT value falling within ranges of central laboratory upper limit of normal (ULN) of:
 - >3x ULN and ≤5x ULN
 - >5x ULN and ≤10x ULN
 - >10x ULN and ≤20x ULN
 - >20x ULN
- Peak AST value falling within ranges of central laboratory ULN of:
 - >3x ULN and ≤5x ULN
 - >5x ULN and ≤10x ULN
 - >10x ULN and ≤20x ULN
 - >20x ULN
- Peak total bilirubin within ranges of central laboratory ULN of:

- <ULN
- >ULN and <2x ULN

- ≥2x ULN
- Peak ALP of >1.5 x ULN
- Simultaneous ALT or AST >3x ULN and total bilirubin >1.5x ULN
- Simultaneous ALT or AST >3x ULN and total bilirubin >2x ULN

For qualitative laboratory values such as urinalysis data, shift tables comparing baseline results (for example, negative, trace, positive) to the worst post-baseline results will be presented.

Listings of laboratory results for each subject will be presented by type of laboratory test and parameter. Values outside of the corresponding reference range will be flagged in the listings. Laboratory values assessed as part of screening (i.e., infectious disease assessments and screening biomarker values) and pregnancy test results will be presented in by-subject listings but will not be summarized.

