3.2. Safety Endpoints

The primary study objective of assessing safety and tolerability of ALPN-101 will be evaluated using the endpoints listed in below:

- Treatment-emergent adverse events (TEAEs), treatment-emergent adverse events of interest (AEIs; infusion-related reactions, oral mucocutaneous lesions, infections grade ≥3), and serious adverse events (SAEs)
- Abnormal laboratory test results and observed and change/shift from baseline in over time for:
 - Chemistry
 - Hematology
 - Coagulation
 - Urinalysis
- Abnormal vital signs results and observed and change/shift from baseline over time for:
 - Systolic and diastolic blood pressures (mmHg)
 - Heart rate (bpm)
 - Respiratory rate (bpm)
 - Body temperature (°C)
 - Weight (kg)
- Abnormal electrocardiogram (ECG) parameters and observed and change/shift from baseline over time for:
 - Heart rate (bpm)
 - QT interval (msec)

- PR interval (msec)
- ORS duration (msec)
- RR interval (msec)
- QTcB interval (msec)
- QTcF interval (msec)

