15.5. Laboratory Assessments

All per-protocol laboratory assessments will be performed by the central lab per the assessment schedule shown in Table 14. Investigators must document their review of each laboratory safety report.

Table 14: Clinical Laboratory Assessments

Assessment	Parameters
Safety:	Platelet count
Hematology	RBC count and indices: MCV, MCH, percent reticulocytes
	WBC count with differential; neutrophils, lymphocytes, monocytes, eosinophils, basophils
	Absolute neutrophil count and lymphocyte count; CD4 and CD8 lymphocytes
	Hemoglobin
	Hematocrit
Safety:	Electrolytes: sodium, potassium, chloride, bicarbonate
Clinical Chemistry	Other cations: calcium, magnesium, phosphorus
	Amylase
	Lipase
	Glucose
	CPK
	LDH
	Renal function: creatinine, eGFR
	Liver Function Tests: ALT, albumin, alkaline phosphatase, AST, total and direct bilirubin, total protein
Safety: Coagulation	PT (i.e., INR), aPTT
Safety: Urinalysis	Specific gravity, pH, glucose, protein, blood, ketones, bilirubin, urobilinogen, nitrite, leukocyte esterase, microscopic examination if blood or protein is abnormal, UPCR
Infectious Disease	Hepatitis B and C viruses, Human Immunodeficiency Virus, tuberculosis, SARS-CoV-2
Other Tests	TSH, FSH and estradiol (female subjects only, if needed to confirm menopausal status)
Clinical Biomarkers of SLE	Screening only: ANA, anti-Smith antibodies, anti-SSA antibodies, anti-SSB antibodies, anti-RNP antibodies, Scl 70 (topoisomerase 1) antibodies, centromere antibodies, anticardiolipin antibodies (IgG and IgM), LAC, anti-beta-2-glycoprotein I antibodies All applicable visits: hsCRP, complements (C3, C4, CH50), quantitative IgM, IgG, IgA, IgE, dsDNA antibodies

Notes:

ALT=Alanine aminotransferase; ANA=Anti-nuclear antibodies; aPTT=Activated partial thromboplastin time; AST=Aspartate aminotransferase; C3=Complement component 3; C4=Complement component 4; CD=Cluster of differentiation; CH50=Total complement; CPK=Creatinine phosphokinase; dsDNA=Double stranded DNA eGFR=Estimated glomerular filtration rate; FSH=Follicle stimulating hormone; hsCRP=High-sensitivity C-reactive protein; INR=International normalized ratio; LAC=Lupus anticoagulant; LDH=Lactate dehydrogenase; MCH=Mean corpuscular hemoglobin; WBC=White blood cell; MCV=Mean corpuscular volume; PT=Prothrombin time; RBC=Red blood cell;

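### SAP 7.8.2 analyses a `<x` safety laboratory result as x minus 1 whatever the unit, which gives impossible negative values wherever the reporting limit is below 1

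*SAP*

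**What the plan says.** The rule in SAP 7.8.2 (Laboratory Tests) covers "Numeric laboratory results that are reported using non-numeric qualifiers, such as less than (<) a certain value or greater than (>) a certain value". Such a result "will be analyzed using the numeric portion of laboratory values minus one or plus one, respectively". So `<x` is analysed as x - 1 and `>x` as x + 1. The section makes no exception by analyte, unit, decimal precision or size of limit.

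The substituted values feed the next paragraph of the same section: "Descriptive summaries of continuous laboratory values and changes in these values from baseline will include the number of non-missing observations, mean, SD, median, min" and maximum, by scheduled visit, at the last on-treatment visit and at the end of study. On units it says only "Data will be summarized in standardized units". It does not list those units or say whether the 1 is subtracted before or after conversion.

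SAP 3.2 places laboratory data among the endpoints for the primary safety objective: "Abnormal laboratory test results and observed and change/shift from baseline in over time for" chemistry, hematology, coagulation and urinalysis. The analytes in SAP 15.5, Table 14, include total and direct bilirubin and "WBC count with differential; neutrophils, lymphocytes, monocytes, eosinophils, basophils".

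Nothing elsewhere overrides the rule. SAP 13 (Data Handling) does not mention qualified laboratory results. The instruction in SAP 7.10 to treat values below the quantitation limit as missing applies to ALPN-101 concentrations only.

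**The concern.** A fixed constant of 1 has no common meaning across analytes measured on different scales. On a scale where typical values are in the tens it is a small adjustment. On a scale where typical values are below 1 it is larger than the measurement, and it moves the result below zero, where the true value cannot be.

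The outcome also depends on the unit. The same sample can be impossible in one unit and nearly unaltered in another, so the table would depend on a choice that the SAP leaves unstated.

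At stake is whether the means, SDs, minima and changes from baseline can be read for the affected parameters. A single such result makes the tabulated minimum impossible. A subject who moves across the reporting limit shows a change created mostly by the rule.

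**Working it through.** The plan states no figure for this rule, so there is nothing to reproduce. The check applies the rule as written and compares it with what is possible.

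**Inputs.** From SAP 7.8.2: `<x` becomes x - 1. From the nature of the measurement: a non-negative analyte reported as `<x` has a true value from 0 up to x. The limits, quantified means and shares below the limit used here are assumptions, because the documents give none.

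**Single values**

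| Reported | Value under the SAP | Possible? | Smallest error, 1 - x |
|---|---|---|---|
| `<0.05` | -0.95 | no | 0.95 |
| `<0.1` | -0.90 | no | 0.90 |
| `<0.5` | -0.50 | no | 0.50 |
| `<0.9` | -0.10 | no | 0.10 |
| `<1` | 0 | yes | none |
| `<2` | 1 | yes | none |
| `<5` | 4 | yes | none |

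Every limit below 1 fails and every limit of 1 or more gives a feasible value. On the upper side, x + 1 is always feasible, although the size of the addition still depends on the unit.

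**Unit dependence.** Exclusion criterion 8b in Protocol 5.2 writes one neutrophil threshold both as 1000/µL and as 1.0 x 10^9/L. It is an eligibility threshold, used here only to show the two scales. A result reported as below that number would be analysed as 1000 - 1 = 999/µL in one unit and as 1.0 - 1 = 0 in the other.

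**Visit means.** Let f be the share of results below the limit and m the mean of the quantified results.

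- Mean under the SAP = f(x - 1) + (1 - f)m
- Lowest feasible mean = (1 - f)m, with every below-limit result at 0
- Highest feasible mean = fx + (1 - f)m

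For x = 0.1, m = 0.2 and f = 10%, the SAP mean is 0.1 x (-0.9) + 0.9 x 0.2 = 0.090.

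| x, m | Share below limit | SAP mean | Lowest feasible | Highest feasible |
|---|---|---|---|---|
| 0.1, 0.2 | 5% | 0.145 | 0.190 | 0.195 |
| 0.1, 0.2 | 10% | 0.090 | 0.180 | 0.190 |
| 0.1, 0.2 | 20% | -0.020 | 0.160 | 0.180 |
| 0.1, 0.2 | 50% | -0.350 | 0.100 | 0.150 |
| 0.5, 0.8 | 5% | 0.735 | 0.760 | 0.785 |
| 0.5, 0.8 | 10% | 0.670 | 0.720 | 0.770 |
| 0.5, 0.8 | 20% | 0.540 | 0.640 | 0.740 |
| 0.5, 0.8 | 50% | 0.150 | 0.400 | 0.650 |

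The gap below the lowest feasible mean is f(1 - x). Enrollment stopped at 76 (SAP 4.1), which is about 38 per arm. One `<0.1` result among 38 therefore lowers an arm mean by at least 0.9/38 = 0.024.

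**Change from baseline.** A move from 0.2 to `<0.1` is tabulated as -0.9 - 0.2 = -1.1, while the true change lies between -0.2 and -0.1. A move from `<0.1` to 0.1 is tabulated as 0.1 - (-0.9) = +1.0, while the true rise is at most 0.1.

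**Between arms.** With the same quantified mean in both arms, the rule contributes (difference in shares) x (x - 1 - m). Equal shares contribute nothing. If 10 percentage points more results fall below the limit in one arm, the contribution for x = 0.1 and m = 0.2 is 0.1 x (-1.1) = -0.11. If below-limit results instead had a common value between 0 and 0.1, it would lie between 0.1 x (-0.2) = -0.02 and 0.1 x (-0.1) = -0.01.

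**The case against.** The strongest answer is that the documents never show the problem occurring. They give no central laboratory reporting limits or analysis units, and no sign that bilirubin, eosinophils or basophils are ever reported with a less-than sign. Table 14 only names analytes. If bilirubin is summarised in µmol/L, 0.1 mg/dL is about 1.7 (a standard conversion, not in the documents). Subtracting 1 after conversion then gives about 0.7, a possible value. This stands: the affected analytes and the frequency are unknown, and the means above are scenarios. It does not rescue the rule, which fails at any limit below 1 and has no safeguard.

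A reader might infer that the primary safety assessment as a whole is compromised. The documents do not support that. SAP 7.8 says "No formal inference is planned". Laboratory safety is also read from CTCAE worst grades, hepatic categories in multiples of the upper limit of normal, shift tables for qualitative results, listings with out-of-range flags, and clinically significant changes recorded as adverse events (SAP 7.8.1 and 7.8.2). A very low bilirubin stays below the upper limit of normal whether analysed as -0.9 or 0.05. Medians are largely protected, because below-limit results rank lowest under either convention. The rule is the same in both arms, so it distorts a comparison only if the shares below the limit differ.

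A reader might also infer that percent change in the SLE biomarkers could have a negative denominator. That is not supported either. The rule sits in the safety laboratory section, which covers hematology, chemistry, coagulation and urinalysis. Percent change is specified for biomarkers (SAP 3.3 and 7.9), and nothing says that the rule applies to them.

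**Conclusion.** The rule is wrong as written, and the consequence is minor. For any non-negative safety laboratory parameter with a reporting limit x below 1 in its analysis unit, it assigns an impossible negative value, in error by at least 1 - x, and the result depends on an unstated unit. The damage is to the mean, SD, minimum and change from baseline in descriptive tables that serve the primary safety objective.

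The error in a single value follows from the SAP's wording alone. Its effect on the tables rests on two assumptions: that some analytes have limits below 1 in the unit used, and what share of results falls below them. Across the assumed scenarios, the mean falls short of its lowest feasible value by between 0.025 (limit 0.5, 5% below: 0.760 - 0.735) and 0.45 (limit 0.1, 50% below: 0.100 + 0.350). If no such result occurs, no negative value arises.

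**What to change.** Replace the sentence in SAP 7.8.2 with one scale-free rule for safety laboratory data. For example: *a result reported as below a limit x is analysed as x/2, and one reported as above a limit x is analysed as x; the result as reported, with its qualifier, is shown in the listings.*

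Half the limit is a convention; the limit itself would also do. Either keeps every below-limit value between 0 and x. Either also gives the same answer before or after a multiplicative unit conversion, so the order of steps no longer matters. In the scenario with limit 0.1, quantified mean 0.2 and 10% below the limit, the mean becomes 0.1 x 0.05 + 0.9 x 0.2 = 0.185 with x/2, or 0.190 with x, both within the feasible range.

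The cost is one sentence and one line of code, with no new data. If the SAP is already final, its Section 8 allows the change to be made by SAP amendment or described in the Clinical Study Report. No change to SAP 7.9 is needed on this account.

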9.1. Adverse Event Definition

An AE is any untoward medical occurrence associated with the use of a drug in a patient or clinical trial participant, whether or not considered drug-related. An AE can therefore be any unfavorable and unintended sign (including an abnormal laboratory finding, for example), symptom, or disease temporally associated with the use of a drug, whether or not considered related to the drug (i.e., does not imply any judgment about causality).

In the context of a clinical trial, AEs include exacerbation of a pre-existing illness or symptom, an increase in frequency or intensity of a pre-existing episodic event or condition, or a condition detected or diagnosed after investigational product administration even though it may have been present prior to the start of the study.

Events that do not meet the definition of an AE include:

- Medical or surgical procedures (e.g., endoscopy, appendectomy); the condition that leads to the procedure should be reported as an AE if applicable;
- Situations where an untoward medical occurrence did not occur (e.g., social and/or observational and/or convenience admission to a hospital);
- Anticipated day-to-day fluctuations of pre-existing disease(s) or condition(s) present or detected at the start of the study that do not worsen.

Abnormal laboratory values or test results constitute AEs if they are clinically significant and/or induce clinical signs or symptoms, or if they require intervention or therapy. Wherever possible, the clinical rather than laboratory term should be reported (e.g., "anemia" rather than "low hemoglobin").

Signs, symptoms, or the clinical sequelae of a suspected overdose of either study drug or a concomitant medication should also be reported as AEs (overdose per se will not be reported as an AE/SAE).

For this study, **signs and symptoms of SLE activity are not to be reported as AEs**, but should be captured in activity assessment tools. However, if SLE symptoms meet SAE criteria (see §9.3), expedited reporting requirements apply as per §9.4.

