6.4. Treatment-Emergent Adverse Events

TEAEs are defined as AEs that start or worsen in severity on or after the administration of the first dose of study drug through the end of study participation or at least 8 weeks after last study drug administration for subjects who discontinue treatment early.

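### The graded laboratory table in SAP 7.8.2 cannot count subjects who enter with an abnormal value and worsen, and for most numeric tests no other count by grade is specified

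*SAP*

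**What the plan says.** SAP 7.8.2 grades laboratory results by CTCAE, sets normal ungraded values to Grade 0, and then states: "Treatment-emergent abnormal laboratory values are defined as those reported normal (i.e., grade=0) at baseline and abnormal (grade 1-4) after starting study medication". The table built on this definition shows, for each parameter, the worst treatment-emergent grade per subject up to the end of the study. Its denominator is wider than its numerator: "Percentages will be based on the number of subjects in the safety population with at least one post-baseline value of the respective laboratory parameter".

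The other laboratory outputs in that section are:

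- **Numeric tests:** mean, SD, median, minimum and maximum of values and of changes, at each scheduled visit, the last on-treatment visit and the end of study. No grades are involved.
- **ALT, AST, total bilirubin and ALP:** counts of peak values by multiples of the upper limit of normal, with no condition on baseline.
- **Shift tables:** specified for non-numeric results only ("For qualitative laboratory values such as urinalysis data, shift tables comparing baseline results", set against the worst post-baseline result).
- **Listings:** by subject, with out-of-range values flagged.

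SAP 3.2 promises more. It lists "Abnormal laboratory test results and observed and change/shift from baseline in over time for" chemistry, hematology, coagulation and urinalysis. Protocol 10.5.5 also names the incidence of clinically significant laboratory abnormalities as a safety endpoint. Neither describes a table by grade.

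On the adverse event side, SAP 6.4 defines treatment-emergent events as "AEs that start or worsen in severity" after the first dose. SAP 7.8.1 says: "Clinically significant changes in physical exam findings, laboratory test results, and ECG results will be recorded and analyzed as AEs".

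SAP 7.8.2 also says that a result reported only as below a limit is analysed as that limit less 1, and one reported as above a limit as that limit plus 1.

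**The concern.** Safety and tolerability are the primary objective, and SAP 7.8 summarizes safety descriptively with no formal inference. The counts are therefore the result. For numeric hematology, coagulation and non-hepatic chemistry, the worst-grade table is the only count by laboratory grade that the SAP specifies. It leaves out the subjects with the least reserve: those who start with an abnormal value and get worse. A move from Grade 1 to Grade 3 or 4 is a non-event in that table.

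The laboratory rule is also stricter than its neighbours. Treatment-emergent adverse events include worsening (SAP 6.4). The absolute QTcF thresholds (SAP 7.8.4) and the blood pressure categories (SAP 7.8.3) carry no normal-baseline condition.

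**Working it through.** The plan gives no figure to reproduce, so the check is of the text, followed by an illustration on assumed inputs.

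**1. Which grade changes are counted.** Under the SAP 7.8.2 definition, Grade 0 to Grade 1, 2, 3 or 4 counts. Grade 1 to 2, 3 or 4, Grade 2 to 3 or 4, and Grade 3 to 4 do not. If a share q of subjects has baseline Grade 1 or higher, the largest percentage the table can show is 1 − q.

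**2. Whether abnormal baselines can enter.** Protocol 5.2 excludes only hemoglobin below 8.0 g/dL, neutrophils below 1.0 × 10⁹/L, platelets below 50,000/µL and eGFR below 40. It sets no coagulation limit among the laboratory exclusions. It waives the transaminase limit when CPK is raised in active myositis, so it foresees an abnormal baseline CPK. SAP Table 11 assigns BILAG grade C to hemoglobin 8–10.9 g/dL and platelets 50–149 × 10⁹/L, and both ranges are admissible. The documents print neither the CTCAE laboratory thresholds nor the laboratory's reference ranges, so these ranges are not converted to CTCAE grades here.

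**3. Illustrative size.** Two inputs are assumptions, because the documents give neither:

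- q: share with an abnormal baseline
- k: risk of worsening with an abnormal baseline relative to a normal one

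Missed share of all worsening: m = qk / (1 − q + qk).

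Enrollment stopped at 76 (SAP 4.1), so 76 / 2 = 38 per arm. At an assumed true incidence of 10%, 38 × 0.10 = 3.8 subjects per arm worsen. The expected reported count is 3.8 × (1 − m).

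| k | q = 10% | q = 30% | q = 50% |
|---|---|---|---|
| 0.5 | m = 0.05/0.95 = 5.3%; 3.6 reported | 0.15/0.85 = 17.6%; 3.1 | 0.25/0.75 = 33.3%; 2.5 |
| 1 | 10%; 3.4 | 30%; 2.7 | 50%; 1.9 |
| 2 | 0.2/1.1 = 18.2%; 3.1 | 0.6/1.3 = 46.2%; 2.0 | 1.0/1.5 = 66.7%; 1.3 |

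**4. Effect on the comparison between arms.** If q and k are the same in both arms, both incidences shrink by the factor 1 − m. With true incidences of 15% and 5% and k = 1, the 10-point difference is reported as 10 × (1 − q) = 9, 7 or 5 points at q = 10%, 30% or 50%. The risk ratio stays at 15/5 = 3.0.

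If k differs between arms, the direction is not fixed. Take q = 30% in both arms:

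- *Overstated.* Normal-baseline risks 15% vs 5%, abnormal-baseline risks 5% vs 15%. True incidences are 0.7 × 15 + 0.3 × 5 = 12% and 0.7 × 5 + 0.3 × 15 = 8%, a difference of 4 points. The table shows 0.7 × 15 = 10.5% and 0.7 × 5 = 3.5%, a difference of 7 points.
- *Erased.* Normal-baseline risk 5% in both arms, abnormal-baseline risks 15% vs 5%. True incidences are 0.7 × 5 + 0.3 × 15 = 8% and 0.7 × 5 + 0.3 × 5 = 5%, a difference of 3 points. The table shows 3.5% in both arms, a difference of 0.

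**5. The minus-one rule (separate, minor).** Subtracting 1 makes any lower reporting limit below 1 negative; an assumed limit of 0.5 becomes 0.5 − 1 = −0.5. Summarizing in standardized units fixes one unit, but the effect still depends on which unit is chosen.

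**The case against.** Counting only new abnormalities is a transparent convention with a stated denominator, and the SAP has other outputs. Several points stand:

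- The data are not lost. The minimum and maximum of values and of changes show the extreme result by arm at each summarized visit, whatever the baseline grade. Listings flag out-of-range values.
- Clinically significant changes become CTCAE-graded adverse events under a rule that includes worsening. Protocol 9.1 also makes a laboratory change an adverse event if it causes symptoms or needs treatment, and investigators must document review of each laboratory safety report.
- SAP 3.2 and Protocol 10.5.5 list relevant endpoints with no Grade 0 condition.
- Some worsening appears in efficacy counts. A platelet fall from the BILAG C to the B range gives a new B grade, which counts towards flare.

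These narrow the gap but do not close it. Minima and maxima are not incidences, and listings give no rate by arm. SAP 3.2 names a shift endpoint for which 7.8.2 gives no method in numeric tests. The adverse event route rests partly on investigator judgement and on attribution, since "signs and symptoms of SLE activity are not to be reported as AEs" (Protocol 9.1) and, likewise in the SAP, "signs and symptoms of SLE activity are captured in the disease activity assessments and will not be reported as AEs". The attribution risk is residual: the SLEDAI-2K thrombocytopenia and leukopenia items (SAP Table 9) set aside drug causes.

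A reader might infer that SAP 6.4 and 7.8.2 contradict each other. They do not: 6.4 governs adverse events and 7.8.2 laboratory grades. It is an inconsistency of approach.

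**Conclusion.** The point holds for graded laboratory incidence in numeric hematology, coagulation and non-hepatic chemistry. In that table the incidence of graded worsening is understated whenever a subject with an abnormal baseline worsens.

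The size is unknown. The range of 5% to 67% missed, or 3.8 expected subjects per arm reported as 3.6 down to 1.3, rests entirely on assumed q, k and a 10% incidence. With few events per arm, one or two uncounted subjects can change how a descriptive table reads.

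Three stronger readings are tempting, and the documents do not support them:

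- *Worsening from an abnormal baseline goes unreported.* It remains partly visible in adverse events, per-visit summaries and listings.
- *The table always understates the treatment difference.* That holds, with the risk ratio unchanged, if the abnormal-baseline share and its relative risk are equal in both arms; otherwise the distortion can go either way.
- *The minus-one rule materially alters the results.* No reporting limits are given, so no material effect is shown. The neutrophil limit in Protocol 5.2 is an eligibility threshold, not a reporting limit, and cannot serve as an example.

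The change is worth making because safety is the primary objective and the correction uses data already collected.

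**What to change.** In SAP 7.8.2:

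1. Define a treatment-emergent laboratory abnormality as any post-baseline CTCAE grade higher than the subject's baseline grade, and tabulate the worst grade on that basis. The present denominator then fits the numerator.
2. Add baseline-to-worst-grade shift tables for numeric hematology, chemistry and coagulation. This supplies the missing method for the shift endpoint listed in SAP 3.2 and lets a reader separate new abnormalities from worsened ones.
3. Separately, analyse results below or above a reporting limit at the limit itself.

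The cost is one revised definition, one added table type and one replaced sentence, with minor programming. SAP section 8 already provides for an SAP amendment.
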